## Inclusion and exclusion criteria

- Inclusion criteria
  - o Mother / birthing parent aged 16 or over.
  - o Mother / birthing parent must have parental responsibility for baby
  - o Mother / birthing parent is registered with a GP in England
  - o Singleton birth

For those with complicated births or early postnatal periods, for example where admission to NICU is necessary, final sampling decisions will be made on a case-by-case basis at the discretion of the research staff and with the NHS clinical team - as well as consent from the parent(s). Births from an egg or sperm donor are eligible, provided the pregnant person will also have full parental responsibility.

- Exclusion criteria
  - Mother / birthing parent under 16
  - Mother / birthing parent who will not have parental responsibility for the baby (Babies who are being adopted)
  - o Mother / birthing parent lacking capacity to provide informed consent for any reason
  - o Mother / birthing parent who do not give birth in one of the recruiting hospitals
  - o Mother / birthing parent who do not have an NHS number
  - o Mother / birthing parent who is serving time in prison

In the initial rollout of the study we will exclude multiple births. We will seek to include these in the study as soon as our core processes are established and we feel the processes are robust enough to support them.

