# Secondary sample - Heel Prick

- Can be obtained from babies born in hospital and those born at home, where it has not been possible to collect cord blood
- The sample should be taken as close to Day 0 as possible.
- Heel prick sampling will be at the discretion of sites and depending on capacity. Heel prick sampling must not take place on the same day as the Newborn Blood Spot test is carried out (usually day 5)
- Before a heel prick is taken, parents should be informed the cord blood has not been collected. The risks of the heel prick (mainly brief pain for the baby) should be explained.
- Parents should be invited to opt-out of a heel prick, however must be made aware that this would also constitute a withdrawal from the study as we will not have a sample to sequence.
- The blood may be collected into an EDTA capillary tube or an EDTA microtainer.
- The latest a sample can be taken AND registered is 28 days after birth. After 28 days the participant will be automatically withdrawn from the study if no sample has been registered and will be issued communication to reflect this, from Genomics England.

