# Condition(s) suspected results

#### Turnaround time

The target 'sample to answer' turnaround time for 'condition(s) suspected' results for the bulk of the programme is 14 days or less i.e., the time from taking the sample on Day 0 to the time that parents are contacted about the result. We aim to achieve within first 9 months of programme starting. The target sample to answer turnaround time at the start of the programme will be 28 days.

This timeline reflects that most conditions will require urgent follow-up testing and treatment. Some babies may already be showing symptoms of the condition at this point and already receiving care.

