The model is structured in two phases. The first phase, a decision tree (shown below), considers the initial screening process and is used to define distinct groups of patients based on the outcome of screening. In the second phase, these groups of patients then progress through one of three distinct Markov models, each simulating a specific post-screening pathway. For the first phase, a weekly-cycle length is used to capture the costs associated with the screening tests, the sequencing process, the interpretation of the screening results and finally the cost of confirmatory diagnostic tests. In the second phase, an annual cycle length is applied to all Markov models, with a half-cycle correction implemented, to capture all the relevant costs and benefits that babies accrue as they are followed for a lifetime time horizon.

The first Markov model (Model A) tracks babies affected with a genetic disease but who have not been detected via WGS or blood-spot (false negative), or who were not detected because of non-participation in the screening programme (i.e., parents declined screening). The second Markov model (Model B) tracks babies with a genetic disease detected by WGS or blood-spot (apparent true positive). The third Markov model (Model C) tracks unaffected babies, this includes babies with

negative WGS or blood-spot results, babies with positive WGS or blood-spot results which was subsequently disproved as negative by a diagnostic test (apparent false positive), and finally unscreened babies that did not participate in either screening program and never develop a genetic condition (unaffected). The model includes the positive predictive value (PPV) and negative predictive value (NPV) for both the blood-spot and WGS screening tests, which determine the number of false negatives and false positives in the population.

Apparent true + Markov Model B Condition(s) Clinical pathway & orthogonal testing Genomic Newbor Apparent false Markov Model C Screening + Genetic Condition Markov Model A No condition suspected result orthogonal testing Markov Model C Apparent true Markov Model B Condition(s) Clinical pathway & suspected resul orthogonal testing Standard of Care Apparent false + Newborn Blood-spor - Genetic Conditi Markov Model A No condition suspected result orthogonal testing Genetic Condition Markov Model C Genetic Conditio Markov Model A

Markov Model C

Figure 9- Decision tree for the draft health economic model

Genetic Condition

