Babies diagnosed with a genetic condition at birth, through either blood-spot or WGS will enter Markov model B in the "pre-symptomatic" health state, and those who subsequently receive treatment will continue through to the "asymptomatic-treatment" health state. From here, they will transition to one of three subsequent health states: "asymptomatic-complete response", "symptomatic-partial response", "symptomatic-treatment failure". The model also includes a "symptomatic-symptoms management" health state to reflect patients who will benefit from having a diagnosis, even without treatment initiation and those with uncertain condition status. Transition probabilities between health states are based on treatment efficacy rates, specific to each condition in the model. In addition, specific mortality rates are applied to each health state.

Babies diagnosed with a genetic condition at symptom onset, either due to false negative results or babies in the control arm who have conditions not screened for in the blood-spot test, will enter Markov model A. The health states in this model are similar to those in model B, except for the addition of a "symptomatic-diagnostic odyssey" health state, which captures the period of time between symptom-onset and receiving a diagnosis. In addition, in model A the "asymptomatic-treatment" state is replaced by the "symptomatic-treatment", since treatment will only begin after symptom onset and diagnosis. Despite the similarity in health-states between models A and B, the transition probabilities differ for some conditions due to reduced treatment efficacy when treatment

No Screen

is initiated at symptom onset rather than at birth. As with model B, specific mortality rates are applied to each health state.

Finally, Markov model C captures the progression of unaffected infants (false-positive, true-negative, and unaffected unscreened infants). Only two health states are considered for this model: "unaffected-well" and "death". For false positive patients, harms of a false diagnosis such as anxiety are captured within the first phase of the model, after a confirmatory negative test they are assumed to rejoin the "unaffected" population.

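### The economic model starts every screen-detected true positive as pre-symptomatic because of how the baby was found, although some may already have symptoms when the result arrives; this tilts the modelled QALY gain towards WGS

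*Protocol*

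**What the plan says.** Section 13 (Economic modelling) describes a decision tree that feeds three Markov models. Assignment to Model B follows the screening outcome: "The second Markov model (Model B) tracks babies with a genetic disease detected by WGS or blood-spot (apparent true positive"). The starting state is then fixed: "Babies diagnosed with a genetic condition at birth, through either blood-spot or WGS will enter Markov model B in the 'pre-symptomatic' health state". Those who are treated move on to the asymptomatic-treatment state, and from there to complete response, partial response or treatment failure.

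Model A, which holds the diagnostic-odyssey and symptomatic-treatment states, is for another group: "Babies diagnosed with a genetic condition at symptom onset, either due to false negative results or babies in the control arm" whose conditions the blood spot does not cover. Babies whose parents declined screening also go there. The same section says that transition probabilities differ between Models A and B for some conditions, because treatment begun at symptom onset is less effective than treatment begun at birth.

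Section 11 (Turnaround time) says of the moment when parents are contacted: "Some babies may already be showing symptoms of the condition at this point and already receiving care". On timing it says "The target 'sample to answer' turnaround time for 'condition(s) suspected' results for the bulk of the programme is 14 days or less", and "The target sample to answer turnaround time at the start of the programme will be 28 days". Section 8 sets the outer limit for the back-up heel-prick sample: "The latest a sample can be taken AND registered is 28 days after birth". Section 6 leaves room to sample ill newborns: "for example where admission to NICU is necessary, final sampling decisions will be made on a case-by-case basis".

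**The concern.** The entry rule has one input, the route of detection. Symptom status when the result is returned is not an input, yet the model's own efficacy difference depends on it. A baby found by WGS who is already ill, and whose treatment therefore starts after onset, is modelled as if it had started before. In the control arm, the same baby with a condition outside the blood spot enters Model A, with a diagnostic odyssey and the lower efficacy. Part of the difference between arms would then come from the labelling of the entry state and not from screening.

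Cost-effectiveness against standard of care is a named secondary outcome, and the model reports an ICER for each of six clusters as well as overall. Clusters with early neonatal onset would be affected most.

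**Working it through.** **No figure to reproduce.** The protocol states no QALY gain, no ICER and no share of babies symptomatic at result. The check is therefore structural, followed by an illustration of direction and size.

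**Structure.** Each described route was tested for a treated, screen-detected baby who already has symptoms:
- Model B entry: pre-symptomatic only.
- Model B symptoms-management state: described for babies who benefit from a diagnosis without starting treatment and for those of uncertain status. It does not cover this baby.
- Model B partial-response and treatment-failure states: reached only after asymptomatic treatment.
- Model A: false negatives, unscreened babies, and control-arm babies with conditions outside the blood spot.
- First phase (weekly cycles): captures screening, sequencing, interpretation and confirmatory-test costs, and the harms of false positives. Disease onset before the result is not mentioned.
- Deterministic sensitivity analysis: varies inputs between bounds. Share symptomatic at entry is not a described input.

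No route fits. Section 11 also has a pathway for results on a baby who has already died, including a judgement on whether the suspected condition contributed. The protocol thus foresees disease that precedes the result.

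**Age at result.** A Day 0 cord sample with the 14-day target gives about 2 weeks. If the same target is counted from a back-up sample taken on day 28, 28 + 14 = 42 days, or about 6 weeks.

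**Direction and size of the QALY effect.** Consider N true positives with conditions found only by WGS. Let G be the gain over Model A for a baby who is truly pre-symptomatic, s the share symptomatic at result, and r their gain as a fraction of G.
- Modelled gain: N·G
- Actual gain: N·G·[(1 − s) + s·r] = N·G·[1 − s(1 − r)]
- Ratio, modelled to actual: 1/(1 − s(1 − r))

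Both s and r are assumptions.

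| s | r = 0 | r = 0.5 | r = 1 |
|---|---|---|---|
| 5% | 1/0.95 = 1.053 | 1/0.975 = 1.026 | 1 |
| 10% | 1/0.90 = 1.111 | 1/0.95 = 1.053 | 1 |
| 20% | 1/0.80 = 1.250 | 1/0.90 = 1.111 | 1 |
| 30% | 1/0.70 = 1.429 | 1/0.85 = 1.176 | 1 |

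**Blood-spot conditions.** These babies get the same entry state in both arms, so their misplacement largely cancels. The net bias comes from conditions that only WGS finds.

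**ICER.** Let K be the screening cost per detected case, dC the added cost and dQ the added QALYs of a pre-symptomatic case, and c the cost ratio for a symptomatic case:

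ICER = (K + dC[(1 − s) + s·c]) / (dQ[(1 − s) + s·r])

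Units are arbitrary, with dQ = 10 and s = 20%:
- K = 500, dC = 0, r = 0: modelled 500/10 = 50; corrected 500/8 = 62.5.
- K = 100, dC = 1000, r = 0.5, c = 0: modelled 1100/10 = 110; corrected (100 + 800)/9 = 100.

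Across 12 settings (four pairs of K and dC, three pairs of r and c), the corrected ICER was higher in 11. The exception is the second case above, where the cost of early treatment outweighs the screening cost and symptomatic cases add no cost.

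**The case against.** The best defence is that the model is labelled a draft, is to be iterated with study data and expert input, and has sensitivity and scenario analyses. A separate Evaluation Protocol, not seen here, may say more. This bears on how serious the gap is but does not close it: new data populate existing inputs, and a missing branch stays missing until someone adds it.

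A second defence is stronger. The protocol does not say where the Model B efficacy inputs come from. If they come from screen-detected cohorts, babies symptomatic by the start of treatment may already be averaged in, and a split would count the penalty twice. This stands and must be checked first.

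Several stronger readings are tempting, and the documents do not support them:
- That some babies will certainly be symptomatic. Section 11 says only that some may be, and gives no share.
- That results can be expected as late as 8 weeks. This adds the outer limit of a back-up sample to the start-up target (28 + 28 = 56 days). The 14-day target was to be met within 9 months of starting. Recruitment began in April 2024 and this version is dated December 2025.
- That every detected baby reaches the asymptomatic-treatment state. Only those treated do.
- That a number of misplaced babies follows from the study's sample size. The model gives a population-level estimate and is not run on the study's participants.
- That symptomatic screen-detected babies should simply receive Model A efficacy. Those values belong to children treated after onset and diagnosis, often after an odyssey, so using them outright could over-correct.

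**Conclusion.** The point holds in limited form. The described entry rule conflicts with the protocol's own account of when results arrive and with its own statement about efficacy. Whenever s > 0 and r < 1, the incremental QALY gain is biased towards WGS, provided that the Model B inputs do not already average in symptomatic babies.

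The size is unknown. Under the assumed ranges, the overstatement is about 3% to 43%. The upper end is the case in which symptomatic babies gain nothing from screening, and there is no overstatement if they lose nothing. A reader might take these percentages as the error in total QALYs or in the ICER. They apply only to the early-treatment gain for WGS-only conditions where efficacy depends on symptom status. A reader might also infer that the ICER must worsen once corrected; that is the usual direction but is not guaranteed.

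**What to change.** 1. First establish how the Model B efficacy inputs were derived. If they already include babies symptomatic at treatment start, either separate them or do not apply a further penalty.
2. Split entry to Model B, per cluster, by symptom status when the result is returned. Asymptomatic babies enter as now.
3. Give symptomatic babies a symptomatic-treatment entry state whose efficacy lies between the Model A and Model B values, with Model A as the lower bound. Credit any shortening of the diagnostic odyssey.
4. Estimate the share from the clinical record review that Section 12 (Healthcare records) already plans for every baby with a condition-suspected result. Name symptom status at result as an item to extract, since the listed items cover investigations and interventions only.
5. Vary both the share and the efficacy in the sensitivity analysis, and rely on that range until study data exist.

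The cost is one extra branch and two inputs per cluster, so 2 × 6 = 12 inputs for the six clusters, plus one extraction item. The base-case ICER will probably be less favourable to WGS.

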## Managing uncertainties and psychosocial impact of results

We are targeting high positive predictive value and focussing on conditions where there is a defined NHS pathway and working case definition agreed through the NHS Clinical Assurance Group. Nevertheless, there are ways in which families may experience distress or uncertainty, as is the case with the current NHS screening programme. These include:

- The psychosocial impact of receiving a condition suspected result or diagnosis of a condition
- Where confirmatory testing indicates that the baby does not have the condition (false positive)
- Where confirmatory test results are uncertain, such that a diagnosis cannot be confirmed or ruled out
- Where the onset and severity of symptoms vary or cannot be specifically predicted for each individual
- Where the timing of the initiation of treatment may vary (from immediately to later in infancy or early childhood)
- The wider familial implications, for example:
  - where parents may be carriers for an autosomal recessive condition, impacting future reproductive decisions;
  - o where siblings are also identified to have the condition
  - o where parents are identified to have a health risk (e.g., where a child is diagnosed with Fanconi Anaemia and parents are each heterozygous for a *BRCA2* gene variant, putting them at increased risk of adult-onset cancers where preventative screening is available)

The specialist team will ensure that condition-specific and broader support needs are facilitated, including where a false positive result is identified and the child would not require ongoing medical management. This includes genetic counselling to address the psychosocial, lifelong and familial impact of the result, as well as referrals for other family members where there are health implications for them.

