## Interpretation, reporting and return of results

Data collected during the interpretation and reporting will include decision to report, final variant classification and variant assessment criteria used.

Regional coordinators will oversee collection of data regarding the return of results to parents and the child's ongoing care. This will include the nature, dates and outcomes of confirmatory nongenomic and genomic testing and the clinical assessment of the child's status according to the study's working case definition for each condition- apparent true positive; apparent false positive; uncertain.

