## Economic modelling

GEL is developing an economic model internally for the health economic evaluation. The initial proposals for the model were produced through a collaboration between GEL and external experts, with the model itself developed by an external economic modelling team. GEL continues to liaise with the NSC and other expert teams on the model. We include a description of the model below, noting that it will be iterated and populated as data from the Generation Study and other studies are generated and responding to ongoing expert input and best practice.

The model aims to estimate the costs and benefits of genomic newborn screening alongside current newborn bloodspot screening. The model includes a control arm, current blood-spot test, as well as an intervention arm for the addition of genomic newborn screening. Consent rates for both screening tests are incorporated, resulting in a subset of babies receiving neither screening test.

The model takes a clustering approach, grouping conditions with similar clinical characteristics, clinical pathways and natural histories together. In total the model currently contains six clusters of conditions that have similar characteristics each of which is represented by around ten conditions. This subset of ~60 conditions, representing the 200+ conditions that will be screened for by WGS, was chosen based on prevalence, data availability, and also clinical importance. Within each cluster, condition-specific inputs are obtained for costs, utilities, and mortality rates, and a weighted cluster average is then calculated for each variable based on the relative prevalence of the condition within the cluster. The model is run individually for each of the six clusters and then aggregated to reach a population-level estimate, based on the relative prevalence of each cluster within the overall population. This allows for cost-effectiveness to be estimated both for individual clusters and for the overall group of conditions.

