Specific costs and utilities are applied to each health state in the three Markov models, therefore patients accrue costs and quality-adjusted life years (QALYs) as they pass through the model. In terms of costs, the model considers treatment costs, direct medical costs, and direct non-medical costs (e.g., social care costs). Utility values for health states are adjusted to account for adverse events from treatments.

Initial data inputs in the model have been obtained from a wide range of sources. The majority of inputs have been sourced from published literature and publicly available datasets. In cases where there was a lack of data available, expert clinicians have been consulted to provide assumptions for the model. For healthcare resource use costs, an analysis of HES datasets has been conducted to obtain resource use inputs for each condition in the model. The model has been built to allow for live data from the Generation Study to be incorporated once available.

Discounting is applied in the model, and differential discount rates are used for costs and benefits. Costs are discounted at a rate of 3.5%, whereas benefits are discounted at a rate of 1.5%.

The key outputs of the model include costs, life years, and QALYs for the blood-spot and WGS arms of the model. These outputs are used to calculate an Incremental Cost Effectiveness Ratio (ICER) to evaluate the cost-effectiveness of introducing WGS screening for newborns. As well as overall costs, QALYs, and ICER estimates, the model also produces disaggregate ICERs for each of the six clusters of diseases in the model. This generates insights into the drivers of cost-effectiveness, particularly useful due to the large variation in treatment costs between the six disease categories.

The model also includes deterministic sensitivity analysis (DSA) to explore the effects of uncertainty on the model's results. As part of the DSA, model inputs are varied between their upper and lower bounds, resulting in a range of plausible results rather than single point estimates. Scenario analyses are also performed, for example on discount rates, to explore the effect of methodological uncertainty within the model.

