#### Secondary questions

### **Screening**

- How many screen positive and how many would be expected if it were adopted nationally?
- What proportion of apparent false positive and false negative findings are there in the study according to each condition's working case definition?
- What proportion of babies have uncertain status following orthogonal testing according to each condition's working case definition
- What age are looked for conditions clinically diagnosed and treatment started with genomic newborn screening as compared to standard of care alone?
- What is the prevalence of the conditions looked for in the newborn population?
- What is the level of uptake of the programme and what would the level of uptake of genomic newborn screening be if it were adopted nationally?
- What are the demographic and other factors that determine outcome e.g., percentage apparent true positive findings? (To include diversity including self-reported ethnicity and indices of socioeconomic deprivation).

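### The economic model gives babies of uncertain condition status a symptomatic health state, although their diagnosis is unresolved and they may have no symptoms

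*Protocol*

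**What the plan says.** The model compares two strategies: "The model includes a control arm, current blood-spot test, as well as an intervention arm for the addition of genomic newborn screening". A decision tree sorts babies by screening outcome and three Markov models then follow them for life. Model B "tracks babies with a genetic disease detected by WGS or blood-spot (apparent true positive"). Model A takes affected babies who were missed or not screened. Model C takes unaffected babies and has only two states, *unaffected-well* and *death*.

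Within the description of Model B, the *symptomatic-symptoms management* state is included "to reflect patients who will benefit from having a diagnosis, even without treatment initiation and those with uncertain condition status". On inputs, the section says that "specific mortality rates are applied to each health state" and that "Specific costs and utilities are applied to each health state in the three Markov models".

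Three other places describe the uncertain class:
- Section 11, on managing uncertainties, lists the situation: "Where confirmatory test results are uncertain, such that a diagnosis cannot be confirmed or ruled out".
- Section 12, on interpretation, reporting and return of results, records the child's status in three classes: "apparent true positive; apparent false positive; uncertain".
- Appendix A, under test performance and clinical utility, asks: "What proportion of babies have uncertain status following orthogonal testing".

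**The concern.** Uncertain status describes what is known about the diagnosis. Symptomatic describes the child's health. The model merges the two. A baby with an unresolved result and no symptoms would, on the text as written, receive the utility, cost and mortality of a symptomatic state.

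This affects the comparison between arms. An unaffected baby whom only WGS flags as uncertain enters that state in the intervention arm. In the control arm the same baby is never flagged and stays in *unaffected-well*. The modelled natural history then changes because of a test label rather than because of disease. Cost-effectiveness is a named secondary outcome, and the incremental cost-effectiveness ratio is built from these differences in cost and QALYs.

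**Working it through.** **Consistency of the text.** The protocol gives no figure on this point to reproduce: there is no uncertain share, state utility, state cost, state mortality or ICER. The check is therefore of one part of the text against another.

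1. Section 12 has three outcomes after confirmatory testing. The decision tree has two: the legible labels of Figure 9 show only apparent-true and apparent-false branches after a suspected result. The text lets positive and negative predictive values determine false positives and false negatives, which is also a two-way split.
2. Model B is for babies with detected disease. An uncertain baby has no confirmed disease, yet the state naming them sits in the Model B description. No entry route is given.
3. Transition probabilities between states are said to rest on treatment efficacy. That basis does not describe the resolution of an untreated baby's diagnosis.
4. False positives are handled differently. Their harms are counted in the first phase and they then rejoin the unaffected group. Nothing comparable is described for an unresolved baby who is in fact healthy.
5. Section 11 (Turnaround time) says that some babies may already have symptoms when the result arrives, so others may not.

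**Illustration of size, per 100,000 screened.**

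From the protocol: incidence 1/572 and sensitivity 65% (Section 6); specificity 99.5% and, as an alternative guide, the roughly 2:1 true-to-false ratio from the US study cited in Section 10; benefits discounted at 1.5% with annual cycles and half-cycle correction (Section 13).

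Assumed: 5–20% of suspected babies uncertain; utility decrement 0.10; an 80-year horizon; none of these babies truly affected.

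- True positives: 100,000/572 × 0.65 = 113.6.
- Suspected at 99.5% specificity: 113.6 + (100,000 − 174.8) × 0.005 = 113.6 + 499.1 = 612.8. Uncertain: 30.6 to 122.6.
- Suspected at 2:1: 113.6 × 1.5 = 170.5. Uncertain: 8.5 to 34.1.
- Discounted years over 80 annual cycles: the sum of 1.015^−(t+0.5) for t = 0 to 79 is 46.75. Loss per baby held for life: 0.10 × 46.75 = 4.68 QALYs.
- Discounted years if resolved after two years (a further assumption): 1.015^−0.5 + 1.015^−1.5 = 0.993 + 0.978 = 1.97. Loss per baby: 0.197 QALYs.

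| Basis for suspected babies | Uncertain babies | QALYs lost, lifetime in state | QALYs lost, two years in state |
|---|---|---|---|
| 99.5% specificity | 30.6–122.6 | 143–573 | 6–24 |
| 2:1 true to false | 8.5–34.1 | 40–159 | 2–7 |

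The lifetime column scales in proportion to the decrement: 0.05 halves it and 0.30 triples it. The result thus depends almost entirely on inputs that the protocol does not supply.

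**The case against.** The strongest defence is that the sentence describes a state and does not set an entry rule. The model includes the state to reflect certain patients. The text does not say that every uncertain baby enters it at birth or remains there, and the only entry state named for Model B is *pre-symptomatic*. Given its label, the state could be meant for children who have symptoms but no settled diagnosis. This reading is possible, but it leaves symptom-free unresolved babies with no state at all, so the gap remains in a different form.

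The model is also a draft, to be iterated with expert input and study data. Section 17 expects most suspected results to be definitively resolved, and Appendix A will count the uncertain ones. These points limit the likely size. The planned deterministic sensitivity analysis varies inputs, however, and the one scenario example concerns discount rates. Neither is described as covering this structural choice.

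The illustration can also be criticised, with reason. The 99.5% specificity precedes manual review and the final gene list, so 613 suspected babies is probably high. That is why the 2:1 basis is shown beside it.

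A reader might infer three stronger things that the protocol does not support:
- That the symptomatic state is occupied in the screened arm only. Blood-spot screening is in both arms, blood-spot positives also enter Model B, and Model A's states are described as similar to Model B's with two stated differences that leave this state in place.
- That all uncertain babies lack symptoms. The protocol does not say so.
- That the model has no route from uncertain to confirmed or treated. No transition map is given for this state, and an undescribed transition is not shown to be absent.

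**Conclusion.** The point holds as an inconsistency in the model's structure. The only state named for uncertain babies is a symptomatic one with its own utility, cost and mortality. That does not fit the protocol's definition of uncertain, the stated population of Model B, or a tree without an uncertain branch.

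The asymmetry is specific: uncertain results generated by WGS arise only in the intervention arm, and an unaffected baby not flagged by blood-spot is well in the control arm. For such babies the distortion counts against WGS. For babies who are truly affected, the control-arm counterpart is in Model A and the direction is not determined by the text, so the net direction depends on an unknown mix.

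The size cannot be computed from the protocol. The range of about 2 to 573 QALYs per 100,000 rests on the assumed uncertain share, decrement, time in state and absence of affected babies. It should not be read as an estimate. Nor can it be said to rival the benefit of screening, because no QALY gain per detected case is available for comparison.

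**What to change.** - Add an uncertain branch to the decision tree after confirmatory testing.
- Add an *uncertain, under follow-up* state without symptomatic utility or mortality, carrying observed follow-up cost and any measured parental impact.
- Give it transitions to confirmed (Model B) and ruled out (Model C) at the rates seen in the study.
- Apply the branch and state alike to blood-spot and WGS results, and keep the same underlying disease risk for a given baby in both arms.
- Reserve the symptomatic state for children with symptoms.
- Add a scenario analysis on the uncertain share, including suspected numbers at about 2:1 true to false.

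The cost is small: one branch, one state and its transitions in a model that is still a draft. Regional coordinators already oversee collection of the status. The drawback is that early transition rates will be imprecise and must be shown as a range.
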